11.2. DISPOSITION

The number and percentage of subjects for each of the following categories will be summarized by treatment group:

- Subjects who enrolled in the open-label extension period
- Subjects who discontinued early from the 52-week open-label extension period and reasons for discontinuation
- Subjects who entered the post-treatment safety follow-up period

For Commercial Switch population following categories will be summarized:

- Subjects included in the extension period

The summaries will be presented in a table and subject disposition data will be presented in a listing.

11.3. PROTOCOL DEVIATIONS

Protocol deviations will be categorized as major and minor per the protocol deviation plan (v 1.0 dated 02 December 2022). Protocol deviations include following categories:

- Deviation from inclusion/exclusion criteria (Eligibility and Randomization)
- Deviation in proper subject's consenting (Informed Consent)
- Deviation in the process assessing the study endpoints (Primary and secondary efficacy endpoint analysis)
- Deviations in study procedures (Study procedures for safety and efficacy (other than primary or secondary efficacy study endpoints)
- Deviations from visit schedule (Missing study visit or visit out of window)
- Deviations in Adverse Events reporting and follow-up (Adverse events)
- Deviation in study drug dosing and handling (IP)
- The intake of prohibited medication(s) (Prohibited / restricted medication and procedures)
- ICH/GCP deviations (Other)
- ICH/GCP deviations (Investigational Site staff related)

Major protocol deviations will be summarized by deviation category for all subjects in the full analysis population. A by-subject listing of major protocol deviations will be provided.

11.4. INVESTIGATIONAL PRODUCT ADMINISTRATION

11.4.1. Extent of Exposure

The following parameters of the study drug will be summarized and listed for the extension period:

- Total number of injections received
- Total amount of dose received (mg)
- Cumulative amount of dose received by weeks (mg/week)
- Total duration of treatment (weeks)

Summary statistics per treatment group will be tabulated by dosing group and total for the Safety Analysis Population. For Commercial Switch Population (Japan only), descriptive summary of first dose date of open label extension since the last dose date of commercially available daily somatropin will be included.

11.4.2. Measurement of Treatment Compliance

Descriptive statistics for study drug compliance will be presented by treatment groups for the Safety Analysis Population.

The number of injections and cumulative dose per subject administered and duration of exposure by treatment groups will be summarized. Treatment compliance will be calculated as total number of actual dose received divided by total number of planned dose expected over specified period will also be displayed.

11.4.3. Dose Adjustment

A descriptive table including the frequency and percentages of subjects by each group will be presented for following dose adjustments categories for Titration period and Maintenance period:

- Titration
- AE
- IGF-1
- Rechallenge
- Other

11.5. DEMOGRAPHIC AND BASELINE CHARACTERISTICS

Descriptive summaries of the extension period baseline will be summarized:

- Age (years)
- Age category (< 30, ≥ 30 - ≤ 60 and > 60 years)
- Sex (male, female)
 - Females (on oral estrogen, not on oral estrogen)
- Race
- Ethnicity
- Region
 - North America
 - Europe
 - Asia-Pacific
- Weight (kg)
- Body mass index (BMI) (kg/m²)
 - < 25 kg/m²
 - $25 \leq - < 30$ kg/m²
 - $30 \leq - < 35$ kg/m²

Statistical Analysis Plan
TCH-306EXT

Ascendis Pharma A/S
Page 23 of 31

- $35 \leq - < 40 \text{ kg/m}^2$
- $\geq 40 \text{ kg/m}^2$
- Body mass index (BMI) SDS
- IGF-1, IGF-1 SDS:
 - IGF-1 SDS < -2.0
 - IGF-1 SDS $-2.0 \leq - < -1.0$
 - IGF-1 SDS $-1.0 \leq - < 2.0$
 - IGF-1 SDS $2.0 \leq - < 2.5$
 - IGF-1 SDS $2.5 \leq - < 3.0$
 - IGF-1 SDS ≥ 3.0
- IGFBP-3, IGFBP-3 SDS

11.6. MEDICAL HISTORY

Medical history will be coded using the Medical Dictionary for Regulatory Activities (MedDRA) and will be summarized by system organ class and preferred term for Commercial Switch Population (Japan only). In addition, Medical History in the extension period is inclusive of medical history collected from the main period and interval history collected since the last visit of the main period (Visit 7/Week 38) and will be providing in the listing.

11.7. PRIOR AND CONCOMITANT MEDICATION

Prior medication is defined as any medication started before the date of the study drug administration (medication start date prior to the first dose date) for Commercial Switch Population in the extension period.

Concomitant medication is defined as medication taken on or after the date of the first dose of lonapegsomatropin in the extension period, where the medication end date is on or after first lonapegsomatropin dose date (or ongoing).

Both prior and concomitant medications will be coded by ATC level 4 (Chemical Subgroup) and ATC level 3 (pharmacologic class) using World Health Organization Drug Dictionary (WHO Drug). If a subject took a specific medication multiple times or took multiple medications within a specific therapeutic class, that subject will be counted only once for the coded drug name or therapeutic class in summary tables. Prior and concomitant medications will be summarized overall and by treatment groups in tables for the Safety Analysis Population and will also be presented in a listing.

11.8. PRIOR AND CONCOMITANT PROCEDURES

Prior procedure is defined as any procedure started before the date of the study drug administration (procedure start date prior to the first dose date) for Commercial Switch Population in the extension period.

Concomitant procedure is defined as any procedures taken on or after the date of the study drug administration of lonapegsomatropin in the extension period (procedure end date on or after the dose date [or ongoing]).

Prior and concomitant procedures will be coded using the Medical Dictionary for Regulatory Activities (MedDRA) and will be summarized by overall and by treatment groups in tables for the Safety Analysis Population and will also be presented in a listing.

[figure not shown]
11.9. EFFICACY ANALYSIS

Efficacy analyses will be conducted on the ITT population.

11.9.1. Analysis of Efficacy Endpoints

- Change from baseline of extension period in trunk percent fat (as assessed by DXA) at Week 52.
- Change from baseline of extension period in trunk fat mass at Week 52 (as assessed by DXA)
- Change from baseline of extension period in total body lean mass at Week 52 (as assessed by DXA)

The ANCOVA model used in the TCH-306 main period will be implemented for the analysis of the efficacy endpoints outlined above.

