### 5.1. INCLUSION CRITERIA

Participants are eligible to be included in the trial only if all the following criteria apply:

1. Signing of the trial specific informed consent
2. Completion of the treatment period and Visit 7 assessments of trial [TCH-306](#), including collection and upload of Visit 7 DXA scan
3. Fundoscopy at Visit 7 in trial TCH-306 without signs/symptoms of intracranial hypertension or diabetic retinopathy stage 2 / moderate or above

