### 9.3.3. Efficacy Endpoints

- Trunk percent fat
- Trunk fat mass
- Total body lean mass

Analyses will be performed on observed value and change from baseline (from both **TCH-306** baseline and TCH-306EXT baseline) by treatment received during TCH-306.

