7.2. EFFICACY ENDPOINTS

- Change from baseline in trunk percent fat at Week 52 (as assessed by DXA).
- Change from baseline in trunk fat mass at Week 52 (as assessed by DXA)
- Change from baseline in total body lean mass at Week 52 (as assessed by DXA)

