8.5. BASELINE MEASUREMENTS

Unless otherwise specified, baseline used in this study will be the extension period baseline, defined as the TCH-306 Visit 7 assessments or the last assessment taken on or prior to the first dose of study drug in TCH-306EXT, whichever occurs later considering date and time.

For the subjects that switched from commercially available daily somatropin treatment (Japan only), baseline value is defined as the last measurement on or before the first administration date (if time is not available) of study drug in the extension period.

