10.8. VISIT TIME WINDOWS

All post-baseline visits will be mapped to the post-baseline scheduled visit with the closest target study day for each scheduled assessment with exception of DXA data, [REDACTED] parameters.

If the unscheduled visit is in the middle of two scheduled visits, it will be mapped to the later one. After mapping, if there is more than one visit in the same window, the visit closer to the target assessment day will be used. If more than one visit has an equal distance to the target day, then the later one will be used; if more than one visit occurs on the same day, the time or the sequence number will be used to select the later record. For listings, all data points (as observed) will be included.

Table 2: Analysis Window (All Parameters Except DXA, [REDACTED] Parameters)

[figure not shown]
PERIOD	VISIT	Week	Target Study Day	Study Day Window
Extension	Visit 8	Date of first open label study drug	X1	<=1
	Visit 9	(EXTENSION) Week 4	X1+ 28	(X ₁ +1) - (X ₁ +42)
	Visit 10	(EXTENSION) Week 8	X1+ 56	(X ₁ +43) - (X ₁ +70)
	Visit 11	(EXTENSION) Week 12	X1+ 84	(X ₁ +71) - (X ₁ +101)
	Visit 12	(EXTENSION) Week 17	X1+ 119	(X ₁ +102) - (X ₁ +157)
	Visit 13	(EXTENSION) Week 28	X1 +196	(X ₁ +158) - (X ₁ +231)
	Visit 14	(EXTENSION) Week 38	X1 +266	(X ₁ +232) - (X ₁ +315)
	Visit 15	(EXTENSION) Week 52	X1 + 364	(X ₁ +316) - (X ₁ +413)
Safety follow-up/End of Study		Safety follow-up	Date of last dose + 28 days	(Date of last dose date + 14 days) - (Date of last dose + 49 days)

Study day in the extension period is calculated with respect to the date of the first dose of study drug. X₁= First dose date of Open Label extension in study day in reference to the first dose day from the main period.

For the analysis of efficacy endpoints and [REDACTED] assessed by DXA, following study day window will be used:

- (EXTENSION) Week 12: analysis will be performed based on the assessments performed at the scheduled visit.
- (EXTENSION) Week 52: analysis will be performed based on the assessments performed at the scheduled visit.

If there are more than one DXA assessment in the same visit, the visit closer to the target assessment day will be used. If more than one DXA assessment with an equal distance to the target day, then the later one will be used in the analysis.

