11. STATISTICAL METHODS OF ANALYSES

11.1. GENERAL PRINCIPLES

In general, summaries will be performed descriptively by treatment group. Continuous, quantitative (absolute values at each time point and change from baseline if applicable) variable summaries will include the number of subjects (N) with non-missing values, mean, standard deviation (SD), standard error (SE) of the mean, median, minimum, and maximum values.

Categorical, qualitative variable summaries will include the frequency and percentage of subjects in the particular category. In general, the denominator for the percentage calculation will be based upon the total number of subjects in the study population for the cohorts.

All statistical tests will be two-sided and tested at statistical significant level of 0.05. P-values will be rounded and displayed in three decimals. If a p-value is less than 0.0001, it will be shown in tables as <0.0001. Confidence intervals will be 2-sided 95% confidence intervals, unless stated otherwise.

Unless otherwise specified, all summaries including by-visit summaries will be analyzed for the extension period (52 weeks of treatment) and for the commercial switch population, all analyses will be repeated and analyzed separately.

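### The protocol plans DXA change from both the TCH-306 and the extension baseline; the visible SAP specifies the extension baseline only and gives no reason

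*SAP*

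**What the plan says.** **Protocol.** Section 9.3.3 lists trunk percent fat, trunk fat mass and total body lean mass. It plans observed values and "change from baseline (from both TCH-306 baseline and TCH-306EXT baseline) by treatment received during TCH-306". Section 9.3.1 gives a general rule that baseline is the last assessment before the first extension dose, DXA included. Section 9.3.3 then adds the TCH-306 baseline for these three endpoints specifically. Section 4.2 justifies the design by the long-term picture it gives: 38 weeks in TCH-306 followed by 52 weeks in the extension.

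**SAP.** Section 7.2 defines the three endpoints as change from baseline at Week 52 without naming the baseline. Section 8.5 supplies the default: "Unless otherwise specified, baseline used in this study will be the extension period baseline, defined as the TCH-306 Visit 7 assessments", or a later assessment if one was made on or before the first extension dose. Section 11.9.1 is explicit: "Change from baseline of extension period in trunk percent fat (as assessed by DXA) at Week 52". The same baseline is named for trunk fat mass and total body lean mass. Section 11.1 confines summaries to the 52-week extension unless otherwise specified.

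**The concern.** The SAP is meant to elaborate the analyses outlined in the protocol. Here it narrows them without comment. If no hidden text supplies the second baseline, following the SAP omits an analysis the protocol names for its secondary endpoints.

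For roll-over participants, the visible change analysis starts after 38 weeks of TCH-306 treatment. In the previously treated groups, an extension change near zero fits a maintained benefit and also fits no benefit at all, so the change alone cannot tell them apart. A change from the TCH-306 baseline helps to do so.

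The second baseline supplements the extension baseline and does not replace it. The extension baseline isolates lonapegsomatropin after a switch. Only the Lonapegsomatropin/Lonapegsomatropin group has the full 38 + 52 weeks on lonapegsomatropin.

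**Working it through.** The check is mainly a comparison of texts. The plan states no figure to reproduce.

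**1. Which baselines each document names for DXA change**

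| Source | TCH-306 baseline | Extension baseline |
|---|---|---|
| Protocol 9.3.3 | yes | yes |
| SAP 7.2 | not named | not named (8.5 default applies) |
| SAP 8.5 | no | yes, by default |
| SAP 11.9.1 | no | yes, for all three endpoints |

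SAP 11.9.1 says that the TCH-306 main-period ANCOVA will be used. That does not restore the missing analysis, because the response is still change from the extension baseline.

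**2. Count of change analyses**

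- Protocol: 3 endpoints × 2 baselines = 6.
- Visible SAP: 3 endpoints × 1 baseline = 3, and 3/6 = 50%.
- Counting observed values as well: the protocol names 3 × 3 = 9. SAP 11.1 provides absolute values, so 6 of 9 are visible.

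**3. What the extension DXA baseline is in practice**

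- Protocol 5.1, criterion 2, requires completion of the Visit 7 assessments, "including collection and upload of Visit 7 DXA scan".
- The supplied protocol's schedule has no DXA scan at Screening or V8. The SAP's schedule points to TCH-306 Visit 7 in its DXA row, though that table is broken in the text available.
- SAP 11.6 places Visit 7 at Week 38 of the main period.

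So for roll-over participants the baseline is in effect the Week 38 scan of TCH-306.

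**4. Time covered by the visible change**

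- Treatment weeks: 38 + 52 = 90.
- Inside the visible change: 52/90 = 0.578, or 58%.
- Outside it: 38/90 = 0.422, or 42%.
- Protocol 4.1 allows V8 up to 8 weeks after V7 without a Screening Visit. With an 8-week interval, the span from Visit 7 to extension Week 52 is (52 + 8)/(38 + 8 + 52) = 60/98 = 0.612, or 61% of calendar time.
- For intervals of 0 to 8 weeks the range is therefore 58% to 61%. The interval may be longer if a Screening Visit is done.

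**5. Participants concerned**

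SAP 4 gives 220 from TCH-306 and 13 Japanese participants switching from commercial daily somatropin. 220 + 13 = 233, and 220/233 = 0.944. Up to 94% are affected. The 13 have no TCH-306 baseline and are not.

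These ratios describe coverage only. The documents give no effect size, so the effect on any estimate cannot be stated.

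**The case against.** **Hidden text could close the gap.** SAP numbering goes from 11.9.2 to 11.11, so 11.10 is not shown, and 10.8 blacks out part of a DXA item: "For the analysis of efficacy endpoints and [REDACTED] assessed by DXA, following study day window will be used". The second baseline could sit there. This stands as a limit on certainty. Against it, 11.9.1 is the section devoted to these endpoints, appears unredacted and names one baseline. A by-visit sentence after SAP Table 3 also uses the extension baseline, but it may belong to the section not shown, so nothing rests on it here.

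**The documents may not match.** The SAP implements protocol version 5.0 of 16 June 2022. The supplied protocol lacks the Japanese switch cohort, and its screening rules differ from the SAP schedule. If version 5.0 has no two-baseline sentence, there is no discrepancy. This also stands, and it is the first thing to check.

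**SAP 11.1 is weak support.** It fixes the period summarised, not the reference point. A Week 52 value compared with the TCH-306 baseline is still a summary at an extension visit. This is fair; the point rests on 8.5 and 11.9.1.

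**Little is lost.** Absolute values by group are planned, the Placebo/Lonapegsomatropin group offers a comparison at Visit 7, and for each participant cumulative change is main-period change plus extension change. In part this holds: the data remain available and the loss is recoverable. But adding published means gives no SD or SE, since Var(A + B) = Var(A) + Var(B) + 2Cov(A, B) needs the within-participant covariance. Main-trial means may also include people who did not enter the extension.

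**Conclusion.** The discrepancy holds on the visible text. Protocol 9.3.3 names two baselines for DXA change, the visible SAP specifies one, and no reason is given. Half of the named change analyses (3 of 6) are missing, for up to 220 of 233 participants, and the first 38 of 90 treatment weeks fall outside the analysis.

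Severity is minor. Safety is the primary objective, the DXA endpoints are secondary, protocol 9.1 plans no hypothesis testing, and the data can be recovered.

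Confidence is moderate. The conclusion assumes that protocol version 5.0 carries the two-baseline sentence and that no hidden SAP text implements it.

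**What to change.** 1. Confirm that protocol version 5.0 contains the two-baseline sentence, and point to any SAP text not shown here that implements it.
2. If there is none, add to SAP 7.2, 8.5 and 11.9.1 a descriptive change from the TCH-306 baseline to extension Week 52 for the three DXA endpoints. Show it by TCH-306 treatment group, for roll-over participants only, beside the extension-baseline change.
3. For the Placebo/Lonapegsomatropin and Daily Somatropin/Lonapegsomatropin groups, label it as change across two treatments. Commercial Switch participants keep the extension baseline only.
4. While editing, settle the grouping: protocol 9.3.3 groups by treatment received in TCH-306, SAP 8.6 by treatment randomized.
5. If the analysis was dropped on purpose, say so and justify it in the SAP before database lock.

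The cost is three descriptive tables and a few lines of SAP text, or one sentence of justification. No new data are needed: protocol section 8 keeps each participant's TCH-306 number, so the TCH-306 baseline scans can be linked.

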## 2.3. BENEFIT/RISK ASSESSMENT

In treatment of adults with GHD, lonapegsomatropin is an investigational long-acting prodrug of hGH with a proposed once-weekly dosing regimen designed to overcome the inconvenience and suboptimal compliance of daily hGH injections. The safety and efficacy profiles are anticipated to be comparable to currently approved hGH products for daily use, while maintaining similar exposure ( $C_{max}$  and weekly AUC). Moreover, the exposure to hGH over the weekly dosing interval is anticipated to enhance delivery of hGH into target tissues and optimize efficacy. Obviating the need for daily injections should increase compliance and therefore long-term efficacy, which would be of great benefit to adult patients with GHD. All participants will receive weekly lonapegsomatropin treatment during this trial. Lonapegsomatropin is approved by the FDA for treatment of pediatric GHD.

The safety of the participants will be monitored by the investigators as well as the medical monitors.

Stopping rules have been defined in the protocol. There are no high-risk procedures required and the measurement of the efficacy endpoint by dual-x-ray-absorptiometry (DXA) can be considered standard of care and is only associated with very low X-ray exposure.

In conclusion, the benefit-risk assessment for this trial is acceptable based on nonclinical, already gained clinical experience and safety data in the pediatric populations and the fact that no harming trial procedures are implemented.

More detailed information about the known and expected benefits and risks and reasonably expected AEs of lonapegsomatropin is found in the current version of the Investigator's Brochure, and in the prescribing information for Skytrofa®.

[figure not shown]
[figure not shown]

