## 4. TRIAL DESIGN

### 4.1. OVERALL DESIGN

This is a phase 3 open-label multicenter extension trial designed to evaluate the long-term safety and efficacy of lonapegsomatropin administered once-weekly. The trial participants are adults (males and females) with GHD having completed the treatment period in trial **TCH-306** (foresiGHt). Therefore, participants are either previously treated with lonapegsomatropin, a daily somatropin product, or placebo in trial TCH-306.

The trial duration will up to 60 weeks in total and consist of:

- Screening Period – up to 3 weeks starting at Screening Visit. A Screening Visit is not needed if all inclusion and no exclusion criteria were met at V7 and if V8 occurs  $\leq$ 8 weeks after V7.
- Treatment Period – (52 weeks), consisting of:
  - Dose Titration Period – 12 weeks, three visits
  - Dose Maintenance Period – 40 weeks, four visits
- Follow-up Treatment-free Period – (30-37 days/4-5 weeks), consisting of:
  - Two weeks after the last dose of trial drug: Collection of AEs remotely
  - 30-37 days after the last dose of trial drug: Samples for ADA and pregnancy test (for females of childbearing potential)

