## 9.1. STATISTICAL HYPOTHESES

No formal statistical hypotheses testing will be performed.

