11.9.2. Analyses of Subgroup

Subgroup analyses of the primary efficacy endpoint using the ANCOVA model will be performed. Subgroups will include but not limited to, the subgroups outlined in Table 3.

Table 3: Planned Subgroup Analyses

[figure not shown]
Subgroup Name	Subgroup Levels
Region	North America, Europe, Asia-Pacific; All regions except Japan vs. Japan
Diabetes mellitus Status (at baseline)	Yes, No
Age (years)	< 30, ≥30 - ≤60, > 60
Sex	Male, Female
BMI (kg/m ²)	< 30, ≥ 30
Concomitant oral estrogen at screening	Yes, No
Dosing Group	Group 1: Oral estrogen intake (any age) or < 30 years old Group 2: ≥ 30 to ≤ 60 years old; no oral estrogen intake Group 3: > 60 years old; no oral estrogen intake

[figure not shown]
Statistical Analysis Plan
TCH-306EXT

Ascendis Pharma A/S
Page 25 of 31

The absolute values and mean change from baseline by visit will be presented with descriptive statistics for all treatment groups using the baseline extension period baseline. For subjects switched from syringe to auto-injector during the extension period, the following analysis will be repeated for the subjects who switched from syringe to auto-injector:

- Exposure/compliance
- TEAEs
- Injection site reaction
- Antibody (only positive vs negative)
- Device related PRO

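### SAP 11.9.1 applies the unwritten TCH-306 ANCOVA to change from extension baseline, so its prior-arm contrasts reflect prior treatment rather than concurrent-control efficacy, and it departs from protocol 9.1 and 9.3.3

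*SAP*

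**What the plan says.** **Model and endpoint.** SAP 11.9.1 lists three DXA outcomes, the first being "Change from baseline of extension period in trunk percent fat (as assessed by DXA) at Week 52"; trunk fat mass and total body lean mass follow in the same form. Its only statement of method is "The ANCOVA model used in the TCH-306 main period will be implemented for the analysis of the efficacy endpoints outlined above". The SAP does not write out the terms, covariates, contrasts or missing-data rule of that model.

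**Baseline.** Under SAP 8.5, "baseline used in this study will be the extension period baseline, defined as the TCH-306 Visit 7 assessments", or a later value if one was taken up to the first extension dose. For DXA this is in practice Visit 7: protocol 5.1 makes the Visit 7 scan an entry condition, and the protocol schedule places extension scans only at Weeks 12 and 52.

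**Treatment and groups.** Protocol 2.3: "All participants will receive weekly lonapegsomatropin treatment during this trial". Protocol 4.1: "participants are either previously treated with lonapegsomatropin, a daily somatropin product, or placebo in trial TCH-306". SAP 8.6 defines the groups by randomised TCH-306 arm, with a separate Commercial Switch group.

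**Testing.** Protocol 9.1: "No formal statistical hypotheses testing will be performed". SAP 11.1: "All statistical tests will be two-sided and tested at statistical significant level of 0.05". SAP 11.9.2: "Subgroup analyses of the primary efficacy endpoint using the ANCOVA model will be performed".

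**Which baselines.** Protocol 9.3.3 asks for observed values and change from both the TCH-306 and the TCH-306EXT baseline, by prior treatment. SAP 7.2 (read with 8.5) and SAP 11.9.1 use only the extension baseline.

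**The concern.** A model that compares randomised arms needs arms that differ in treatment over the period measured. Here they do not: the groups differ in what they took during the 38 weeks before extension entry. Change is then measured from a point at which two of the three groups have already been treated with growth hormone and the third has not.

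The secondary objective is the efficacy of lonapegsomatropin. If a between-group difference with a p-value is produced from this model, it can look like an efficacy result when it mainly records what happened before entry. In the case the sponsor would hope for (an effect in TCH-306, maintained in one group and matched by catch-up in the other), the sign is unfavourable to continued treatment. The subgroup ANCOVAs would repeat that pattern in each subgroup. Separately, dropping the TCH-306 baseline removes the output that would show maintenance and catch-up side by side.

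**Working it through.** The plan has no figure to reproduce: protocol 9.5 and SAP 4 both state that no formal sample size calculation was done.

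**Inputs from the documents.** 220 TCH-306 completers (SAP 4); two-sided 0.05 (SAP 11.1); Visit 7 baseline; lonapegsomatropin for all.

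**Assumed, because the documents do not give them.** 73 per group (220/3 = 73.3, equal allocation), with 60 as a lower case; between-subject SD of trunk percent fat 8 points; noise SD s per visit of 1.5 or 2.5 points; TCH-306 effect E of 1, 2 or 3 points; full maintenance in Lona/Lona and full catch-up in Placebo/Lona, so that true Week 52 levels are equal; a Visit 7 covariate in the ANCOVA.

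**Step 1, unadjusted contrast (Lona/Lona minus Placebo/Lona).** The Week 52 difference is 0 and the Visit 7 difference is −E. The contrast in change is 0 − (−E) = +E. For fat, a positive value is unfavourable to continued treatment.

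**Step 2, ANCOVA contrast.** The within-group slope of Week 52 on Visit 7 is λ = 64/(64 + s²), so the slope of change on Visit 7 is λ − 1. The adjusted contrast is E − (λ − 1)(−E) = λE.
- s = 1.5: λ = 64/66.25 = 0.966
- s = 2.5: λ = 64/70.25 = 0.911

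The choice of baseline creates the difference; the covariate shrinks it slightly.

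**Step 3, how often p < 0.05.** Residual variance is 64 + s² − 64²/(64 + s²). For s = 1.5 this is 66.25 − 61.83 = 4.42, SD 2.10, and SE = 2.10 × √(2/73) = 0.348. At E = 1 the ratio is 0.966/0.348 = 2.78, or about 79% rejection. Simulation (1,500 trials per scenario) agrees:

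| E | s | Contrast, 73 per group | p < 0.05, 73 per group | p < 0.05, 60 per group |
|---|---|---|---|---|
| 1 | 1.5 | +0.97 | 79% | 72% |
| 1 | 2.5 | +0.91 | 35% | 30% |
| 2 | 1.5 | +1.93 | >99% | >99% |
| 2 | 2.5 | +1.84 | 89% | 82% |
| 3 | 1.5 | +2.90 | 100% | 100% |
| 3 | 2.5 | +2.74 | >99% | 99% |

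**Step 4, sensitivity.** With s = 4, λ = 64/80 = 0.80, and rejection at 73 per group falls to about 15%, 43% and 75% for E = 1, 2 and 3. With E = 0 the expected contrast is 0 and rejection is about 5%.

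**Step 5, same data from the TCH-306 baseline.** Regressing change from the pre-randomisation value on arm and that value gives a contrast of −0.01 to +0.02 and rejection of 4.2% to 5.8%. Mean change is about −E in both groups, so maintenance and catch-up are both visible.

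**Daily/Lona.** This group was on active treatment at Visit 7. Its contrast with Lona/Lona compares maintenance with switching. The calculation above does not cover it.

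**Document comparison, which needs no assumptions.**

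| Topic | Protocol | SAP |
|---|---|---|
| Efficacy baseline | Both (9.3.3) | Extension only (7.2 with 8.5, 11.9.1) |
| Hypothesis testing | None (9.1) | Two-sided 0.05 convention (11.1) |
| Primary endpoints | Safety (section 3) | Subgroups of a primary efficacy endpoint (11.9.2) |

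**The case against.** **No contrast is written down.** This is correct. That one will be reported, with a Visit 7 covariate and a p-value, is inferred from the imported model and the general 0.05 sentence, which names no test. The same model could be used only for least-squares means per group, which would describe within-group change. The point is therefore about what the text permits, and the silence is part of the problem.

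**Covariate adjustment as the culprit.** A reader might infer that adjusting for a post-randomisation value creates the artefact. For the SAP's endpoint, which is change, it does not: the unadjusted contrast is already the full E, and adjustment reduces it.

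**The drug shown to be worse.** A reader might infer that the plan will show continued lonapegsomatropin as significantly worse than the placebo switch. The documents do not support that. They give no TCH-306 effect, SD or allocation, and the direction needs an effect plus maintenance and catch-up. Under those same assumptions, the fall in the ex-placebo group beside a stable continued group is itself a sign that starting the drug works. What is missing is a concurrent control, and the sign is easily misread.

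**Descriptive output already exists.** SAP 11.1 plans summaries by group and specifies 95% intervals, and the text after Table 3 in 11.9.2 adds values and change by visit. This stands in part: redaction leaves unclear which endpoints that text covers, and it uses the extension baseline only.

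**Conclusion.** The point holds in a limited form. On change from extension baseline, a Lona/Lona versus Placebo/Lona contrast mainly reflects treatment before entry, and Lona/Lona versus Daily/Lona is a maintenance-versus-switch comparison. Neither is a concurrent-control estimate of efficacy. With full maintenance and catch-up the first contrast is E unadjusted and about 0.91 to 0.97 E by ANCOVA under the main assumptions (0.80 E at noise SD 4). Rejection runs from about 15% to 100% across the non-zero effects and noise levels shown, and there is no artefact at E = 0. These sizes are illustrations, not predictions for this trial.

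The departures from protocol 9.1 and 9.3.3, and the reference to a primary efficacy endpoint that the extension does not have, rest on the text alone. Safety is primary, so the trial's main conclusion is not at risk. The plan should still be corrected, because a misleading p-value on the secondary objective is easy to avoid.

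**What to change.** - **SAP 7.2 and 11.9.1:** make the efficacy analysis within-group mean change with 95% CI by prior TCH-306 arm, from both baselines as protocol 9.3.3 requires. Drop between-arm p-values on change from extension baseline. State what each group shows: Placebo/Lona, response after starting; Lona/Lona, maintenance; Daily/Lona, maintenance after a switch.
- **If an arm comparison is kept:** write the model out in full. Compare Week 52 values by randomised TCH-306 arm, adjusted for the pre-randomisation value, and label it descriptive early versus delayed start. Only participants who completed TCH-306 and entered the extension contribute, so randomisation protects it only in part.
- **SAP 11.9.2:** name the endpoint (for example trunk percent fat), delete the word primary, and present subgroups descriptively.
- **SAP 11.1:** align the 0.05 sentence with protocol 9.1.

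No new data are needed for the TCH-306 participants. The cost is SAP wording, a few more tables for the second baseline, and the loss of p-values that the protocol does not plan.
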